Analysis: Testing method, testing history and result, accessibility to testing, and current symptoms will be presented in Table 2. All responses are taken from the Baseline Survey and will be summarized by age category (Adult, Minor, Overall). All categorical variables will be summarized as counts and percentages. The denominators for the percentages for each variable are defined as the number of participants in the Baseline Survey Evaluable Population who have non-missing data for the variable.

- See Appendix for proposed:
 - Table 2: Participant COVID-19 Testing and Symptoms in Baseline Survey in Merced County, CA

- Objective:** Summarize attitudes towards SARS CoV-2 vaccination of participants in the Baseline Survey Evaluable Population

Analysis: Reasons for getting and not getting a COVID-19 vaccine will be presented in Table 3. All responses are taken from the Baseline Survey and will be summarized by age category (Adult, Minor, Overall). All categorical variables will be summarized as counts and percentages. The denominators for the percentages for each variable are defined as the number of participants in the Baseline Survey Evaluable Population who have non-missing data for the variable.

- See Appendix for proposed:
 - Table 3: Participant Attitudes towards SARS CoV-2 vaccination in Baseline Survey in Merced County, CA

4. Objective: Summarize personal protective equipment and distancing information in the work place of participants in the Baseline Survey Evaluable Population

Analysis: Personal protective equipment and distancing information in work place will be presented in Table 4. All responses are taken from the Baseline Survey and will be summarized by age category (Adult, Minor, Overall). All these variables are ordinal, and they will be summarized as counts and percentages. The denominators for the percentages for each variable are defined as the number of participants in the Baseline Survey Evaluable Population who have non-missing data for the variable.

- See Appendix for proposed:
 - o Table 4: Participant Infection Risk in Work Place in Baseline Survey in Merced County, CA

5. Objective: Model the association between sociodemographic factors (i.e., age category, race, ethnicity, and preferred language) and the following outcomes in the Front Door Survey Evaluable Population

- i) reasons for test use,
- ii) test result,
- iii) current vaccination status,
- iv) likelihood of future vaccination,
- v) perceived COVID-19 medication access

Analysis: Sociodemographic factors and outcomes will be drawn from the Front Door Survey. For the outcome i) reasons for test use, we will run a logistic regression model on each of the possible choices since participants could choose all that applied. For the outcomes ii) and iii), logistic regression will be used. For the outcome iv) likelihood of future vaccination, ordinal logistic regression will be used. For the outcome v), we will run a logistic regression model on each of the possible answers. Odds ratio estimates and 95% confidence interval will be presented in Table 6.

The methods described above will constitute the main analysis of these primary outcomes. The hypothesis is defined as:

$$H_0: \beta_i = 0$$

$$H_a: \beta_i \neq 0$$

And the logit is the linear function: $\ln(\frac{P}{1-P}) = \alpha + \beta_1 x_1 + \beta_2 x_2 + \dots + \beta_k x_k$

Where β_i is the parameter coefficient of independent variable x_i , and p represents the true probability that the dependent variable $y=1$ (event) given the numeric values on the independent variables. This analysis will be conducted using PROC LOGISTIC in SAS. The hypothesis as expressed above will be tested at a 2-sided significance level of 0.05.

Crucial assumption that must be met for logistic regression is linearity in the logit for continuous independent variables. We will use the Box-Tidwell test and scatter plot to check for linearity between the continuous predictors and the logit. If the linearity assumption is violated, it is necessary to make further adjustments either to the model (including or excluding predictors), or transforming the response and/or predictors. We will use restricted cubic splines to explore non-linear continuous associations.

It is important to note that the independence assumption for the logistic regression models may be violated since a single participant can enter multiple records in the Front Door Survey, but cannot be distinguished. If the violation is occurring then our models are underestimating standard errors, leading to inflated Type I error.

- See Appendix for proposed:
 - o Table 6: Regression estimates for the association between sociodemographic factors and COVID-19 testing, vaccination, and medication outcomes

6. Objective: Model the association between social determinants of health (i.e., gender identity, employment, food/water/housing insecurity, and health insurance) and the following outcomes in the Baseline Survey Evaluable Population

- i) testing attitude (i.e., Participant thinks it's easy to get tested for COVID-19)
- ii) testing behavior (i.e., Participant has been tested for COVID-19)

Analysis: Social determinants of health and outcomes will be drawn from the Baseline Survey. For the outcome i) testing attitudes (i.e., Participant thinks it's easy to get tested for COVID-19), ordinal logistic regression will be used. For the outcome ii) testing behavior (i.e., Participant has been tested for COVID-19), logistic regression will be used. Odds ratio estimates and 95% confidence interval will be presented in Table 7.

The methods described above will constitute the main analysis of these secondary outcomes. The hypothesis is defined as:

$$H_0: \beta_i = 0$$

$$H_a: \beta_i \neq 0$$

And the logit is the linear function: $\ln(\frac{P}{1-P}) = \alpha + \beta_1x_1 + \beta_2x_2 + \dots + \beta_kx_k$

Where β_i is the parameter coefficient of independent variable x_i , and p represents the true probability that the dependent variable $y=1$ (event) given the numeric values on the independent variables. This analysis will be conducted using PROC LOGISTIC in SAS. The hypothesis as expressed above will be tested at a 2-sided significance level of 0.05

- See Appendix for proposed:
 - o Table 7: Regression estimates for the association between social determinants of health and COVID-19 testing attitude and behavior

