## Purpose of the Study

This is an observational, direct-to-participant sub-study that distributes at-home, self-administered, SARS-CoV-2 antigen testing kits to people in designated communities. Duke will be in charge of the coordination of the sub-study. Adults and children living within the pre-identified communities will be invited to take part in the substudy, provided they meet the inclusion criteria. Potential subjects will self-identify by actively choosing to seek further information about the study via REDCap or by calling the DCRI Call Center. They will be able to participate via REDCap or through the DCRI Call Center. The study will be called You & Me COVID-Free Research Study.

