This cohort sub-study in a subset of the population will explore human factors in response to testing and vaccination. Participants in the public health intervention who meet eligibility criteria will be invited to participate in the sub-study, consented, and asked to complete questionnaires aimed at evaluating self-reported health conditions, COVID-19 testing and symptoms, social interactions, knowledge of prevention strategies, infection risk, and attitudes towards vaccines. This sub-study will provide participant-level information essential to understand COVID-19 testing and vaccination awareness and access and relevant for implementation of public health interventions in future pandemics.

Further details of the background and the design of the study can be found in the study proposal.

Specific Analysis Aims

1. Characterize self-reported COVID-19 testing and symptoms.
2. Delineate attitudes towards SARS CoV-2 vaccination.
3. Describe infection risk in work place.
4. Explore the relationship between sociodemographic factors, i.e., age, race, ethnicity, and preferred language, and
 - a. reasons for test use,
 - b. test result,
 - c. current vaccination status,
 - d. likelihood of future vaccination,
 - e. perspective on easiest way to obtain free oral COVID medicines.
5. Explore the relationship between social determinants of health, i.e., gender identity, employment, food/water/housing insecurity, health insurance, and COVID-19 challenges, and
 - a. testing attitude (i.e., Participant thinks it is easy to get tested for COVID-19)
 - b. testing behavior (i.e., Participant has been tested for COVID-19)

Study Population

The study population will consist of people who meet the following criteria:

- Adult and child residents who are 2 years of age or greater at enrollment
- Self-report primarily residing within the intervention community (Merced County, California)
- Are participating in the public health intervention, regardless of vaccination status

The questionnaire includes three parts:

- Front Door Survey
- Baseline Survey
- End of Study Survey

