A participant could scan a QR code on the participant instruction card or the You & Me COVID-Free bag to access a 1-minute Front Door Survey each time she/he takes a swab test. Individuals will also be invited to complete a more detailed Baseline Survey, which will take about 20 minutes, and then another short follow-up survey (i.e., End of Study Survey) about four weeks later. There is no consent required for each completion of the Front Door Survey and scanning the QR code will start the Front Door Survey automatically. Immediately following the Front Door Survey, the participant is asked if they would like to participate in the sub study. If they agree, they are asked to sign an informed consent form and then given the Baseline Survey to complete. The End of Study Survey is administered 28 days following the completion of the Baseline Survey. The participants who fill out the Baseline Survey and the End of Study Survey will be included in the sub study if they provide a signed and dated informed consent form. There are no exclusion criteria.

As the at-home tests are authorized for children ages 2 and up, these children may also participate in at-home testing, but they will not be enrolled as participants themselves. For children 2 to 14 years of age, an adult must collect the sample and complete the test procedure. Data will be obtained from participants at the individual level.

The Front Door Survey is administered after each swab test by scanning the QR code. There is no consent needed for the Front Door Survey. Immediately following the Front Door Survey, the Baseline Survey is administered at the time of informed consent. The End of Study Survey is administered 28 days following the completion of the Baseline Survey.

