Among 1,208 consented participants in Baseline Survey, no participant completed full set of secondary outcomes, 1,208 participants partially completed secondary outcomes, and no participant were missing all secondary outcomes. See details in Table 2.

Table 2. Missingness of Secondary Outcomes in Baseline Survey

[figure not shown]
	Participant attitudes towards SARS-CoV-2 vaccination		Accessibility to personal protective equipment and distancing in the work place			Self-report COVID-19 testing				Self-report symptoms
	Reasons for getting COVID vaccine	Reasons for not getting COVID vaccine	Have access to necessary facilities to wash	Work require to be in close contact with others	have access to necessary personal protective equipment	Testing method	Have been tested for COVID	Have tested positive for COVID	Accessibility to testing	12 survey items
Missing	0	0	642	643	642	375	216	376	218	275-381
Not missing	1208	1208	566	565	566	833	992	832	990	827-933
Total	1208	1208	1208	1208	1208	1208	1208	1208	1208	1208

Figure 1. Consort Diagram of Front Door Survey and Baseline Survey

Front Door Survey

Baseline Survey

Participants for this sub-study will be recruited within Merced County, California, participating in the larger public health intervention. Recruitment strategies include marketing with public health messaging in collaboration with local health departments, community organizations, media and targeted social media outreach for awareness and education, as well as other strategies that would be tailored to the different distribution scenarios. Participants may be compensated up to \$50 for completion of all surveys. The sample size is up to 300,000 for the sub-study. The test kits distributed as part of the larger study will contain information about the sub-study and how-to consent using either a mobile application (e-consent) accessible free of charge to participants or via phone consenting (verbal consent).

All analyses will be conducted in the evaluable populations corresponding to the Front Door Survey and the Baseline Survey. The Front Door Survey Evaluable Population is defined as entries that have a valid SARS CoV-2 test response (i.e., positive or negative). The Baseline Survey Evaluable Population is defined as participants who were 2 years of age or above at enrollment, consenting to participate in the Baseline and End of Study Surveys.

Intervention

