No imputation will be performed for missing data. Participants who *do not know* or *prefer not to answer* a question used as an outcome variable will be treated as missing data. Survey entries which do not show a valid (positive or negative) SARS CoV-2 test result (N=111) in the Front Door Survey will not be included in the Front Door Survey Evaluable Population. Out of the 2,510 entries in the Front Door Survey, 425 completed survey items on key primary outcomes. Among the 1,313 respondents who consented to participate Baseline and End of Study Survey, 480 completed survey items on key secondary outcomes.

Analysis Objectives and Tasks

- Objective:** Summarize sociodemographic characteristics and medical history of participants in the Baseline Survey Evaluable Population and summarize sociodemographic and test-relevant characteristics of entries in Front Door Survey Evaluable Population

Analysis: Sociodemographic characteristics and medical history summaries will be presented in Table 1. All the sociodemographic characteristics and medical history variables from the Baseline Survey will be summarized by age category (Adult, Minor, Overall) where Adult is defined as age ≥ 18 years of age. Similarly, sociodemographic and test-relevant characteristics of entries will be presented in Table 5. All variables are categorical and will be summarized as counts and percentages. The denominators for the percentages for each variable in Table 1 are defined as the number of participants in the Baseline Survey Evaluable Population who have non-missing data for the variable. The denominators for the percentages for each variable in Table 5 are defined as the frequency of entries in the Front Door Survey Evaluable Population which have non-missing data for the variable.

- See Appendix for proposed:
 - Table 1: Participant Sociodemographic Characteristics and Medical History in Baseline Survey in Merced County, CA
 - Table 5: Sociodemographic and Test-relevant Characteristics in Front Door Survey Entries in Merced County, CA

- Objective:** Summarize self-reported COVID-19 testing characteristics and symptoms corresponding to the Baseline Survey Evaluable Population

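### The SAP contradicts itself on whether minors are in the Baseline Survey population, and Objective 6 (Table 7) would pool any minors with adults without an age limit or age term

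*SAP*

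**What the plan says.** The documents take two positions on children.

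- **Not participants.** SAP, Study Population, on children aged 2 and up: "these children may also participate in at-home testing, but they will not be enrolled as participants themselves".
- **Participants.** The eligibility list in the same section reads "Adult and child residents who are 2 years of age or greater at enrollment", and its closing paragraph states "The Baseline Survey Evaluable Population is defined as participants who were 2 years of age or above at enrollment". The protocol's Purpose of the Study says "Adults and children living within the pre-identified communities will be invited to take part in the substudy, provided they meet the inclusion criteria". SAP Objective 1 plans that Baseline variables "will be summarized by age category (Adult, Minor, Overall) where Adult is defined as age ≥ 18 years of age", and the shells for Appendix I Tables 1 to 3 have a Minor column.

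Objective 6 models "the following outcomes in the Baseline Survey Evaluable Population". One of these outcomes is "testing attitude (i.e., Participant thinks it's easy to get tested for COVID-19"; the other is whether the participant has been tested. Both are tested at a two-sided 0.05 level. The notes to Table 7 name gender identity as the only adjuster. They also limit the respondent base to participants with complete data on the full set of social determinants, including employment.

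Elsewhere the SAP does handle age. The Table 4 shell has an Adult column only, although Objective 4's text says "All responses are taken from the Baseline Survey and will be summarized by age category (Adult, Minor, Overall". Table 6 adjusts for age. Table 1 reports age in years, so Baseline age is collected.

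**The concern.** Two analysts following this SAP could fit Objective 6 to different populations and both be compliant. If children are not enrolled, the age-2 definition and the Minor columns are wrong. If they are enrolled, the Objective 6 models mix minors and adults and have no term to separate them.

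The exposure is clearest for current employment status. The Table 1 shell marks six of its eight levels as not applicable to minors and leaves only *Student* and *Other* (plus missing) open to them. In Table 7, *Other* is the row without an estimate, so it appears to be the reference. Minors in *Student* would alter that one contrast; minors in *Other* would alter every employment contrast. Employment could then stand in partly for age.

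The attitude outcome raises a separate question. A very young child has no answerable opinion on how easy it is to get tested, so a response on such a record could only be an adult's. The SAP gives no respondent rule for minors in the Baseline Survey.

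**Working it through.** **Step 1: the stated counts.** The missingness table for secondary outcomes (SAP, Study Population) gives, for having been tested, 216 missing + 992 not missing = 1,208. For accessibility to testing it gives 218 + 990 = 1,208. Both match the stated 1,208 consented participants. No count is split by age, so neither the number of minors nor an adult-only N can be recovered.

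**Step 2: route into Table 7.** A minor contributes to the current employment comparison only if (a) minors hold Baseline records, (b) the minor is coded *Student* or *Other* rather than missing, and (c) the other social determinants are complete. The documents allow all three and establish none.

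**Step 3: illustration through *Student*.** All inputs are assumed: 84% of adults tested at every employment level (true odds ratio 1.0), 60 adult students, and *m* minors all coded *Student* with tested share *q*. The comparison level contains no minors.

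Pooled share *p* = (*m* × *q* + 60 × 0.84) / (*m* + 60); odds ratio = [*p* / (1 − *p*)] / (0.84 / 0.16), where 0.84 / 0.16 = 5.25.

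- *m* = 60, *q* = 0.70: *p* = (42 + 50.4) / 120 = 0.770; odds ratio 0.64.
- *m* = 150, *q* = 0.70: *p* = (105 + 50.4) / 210 = 0.740; odds ratio 0.54.
- *m* = 150, *q* = 0.78: *p* = (117 + 50.4) / 210 = 0.797; odds ratio 0.75.
- *m* = 150, *q* = 0.95: *p* = (142.5 + 50.4) / 210 = 0.919; odds ratio 2.15.

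Sixty and 150 minors are 60 / 1,208 = 5.0% and 150 / 1,208 = 12.4% of consented participants, or 60 / 992 = 6.0% and 150 / 992 = 15.1% of those who answered the tested item.

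**Step 4: illustration through the reference level.** Again all inputs except the 992 are assumed: 85% of adults tested at every level, 5% of adults in *Other*, half of minors in *Other*, and minors 5% to 30% of respondents. The contrast is *Working now* against *Other*.

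Worked case, 5% minors with 75% tested: adults in *Other* = 942.4 × 0.05 = 47.1; minors in *Other* = 49.6 × 0.5 = 24.8; pooled share = (47.1 × 0.85 + 24.8 × 0.75) / 71.9 = 0.8155; odds ratio = (0.85 / 0.15) / (0.8155 / 0.1845) = 1.28.

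| Minors tested | Odds ratio, 5% minors | Odds ratio, 30% minors |
|---|---|---|
| 60% | 1.75 | 3.09 |
| 75% | 1.28 | 1.70 |
| 95% | 0.74 | 0.42 |

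An adult-only model returns 1.00 by construction in Steps 3 and 4.

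**Step 5: a case with no shift.** If *Student* and *Other* each held 60 adults and equal numbers of minors with the same tested share, the *Student* against *Other* odds ratio would stay at 1.0, while other contrasts against *Other* would move. Size and sign therefore depend on facts the documents do not give.

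**The case against.** The strongest reply is that no minor is shown to be in the data. If the sentence on non-enrolment governs, Objective 6 has no age problem, and what remains is inconsistent wording and empty Minor columns. Minors with missing employment, insurance or housing data would also fall out under the Table 7 notes, and the not-applicable cells are a table layout rather than documented survey logic. Aim 5 is exploratory, and Tables 1 to 3 already show minors and adults separately. All of this stands. It limits what can be said about bias, but it does not settle which population Objective 6 uses.

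Three stronger inferences are not supported.

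- *Parents answered the Baseline Survey for children, so attitude is counted twice within families.* Completion on behalf of a child is described only for the Front Door Survey (notes to Table 5). For the Baseline Survey, the SAP says each participant signs up once and each record represents one participant. No parent-child pairs are documented, and an older adolescent could answer personally.
- *The gap between the 1,313 consented respondents in Handling of Missing Data and the 1,208 in Study Population reflects minors.* The difference of 105 is unexplained and cannot be attributed to age.
- *The All Respondents column of Tables 2 and 3 should become adults only.* That would duplicate the Adult column and contradict the table notes, which define the total as all who consented.

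**Conclusion.** The point holds as a contradiction in current text that reaches a hypothesis-testing analysis. The SAP both excludes and includes children aged 2 and up, and Objective 6 uses the inclusive definition without any handling of age. If minors with complete data are present, the current employment odds ratios could partly reflect age, and a young child's attitude response could only be an adult's.

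A reader might infer from the illustrations that the employment odds ratios are biased, or biased downward. The documents do not support either statement. The number of minors, their employment coding and their tested share are not given. The assumed scenarios run from about 0.42 to 3.09 around a true value of 1.00, and the effect is nil if no minor holds a Baseline record. They are crude odds ratios that show only that moderate numbers of minors could matter. This should be settled before Table 7 is run.

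**What to change.** 1. Reconcile the protocol's Purpose of the Study with the SAP's Study Population section, evaluable-population definition and Objectives 1 to 4 on whether minors hold Baseline records. Report how many do, and state who answers for them.
2. Restrict the main Objective 6 and Table 7 models to participants aged 18 or over, as the Table 4 shell already does. If minors are kept, add age to the models and give an adult-only sensitivity analysis. The sensitivity analysis is needed because minors and adults overlap only in *Student* and *Other*, and because an age term does not resolve who gave the attitude answer.
3. Limit Objective 4's text to adults, to match Table 4.
4. Leave the All Respondents columns of Tables 2 and 3 as they are.

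The cost is one filter (or one covariate and a second run) and some SAP wording. Age is already collected, and the SAP already reports Baseline counts, so the minors should be countable now. The drawback of restriction is that Table 7 loses the minors, whose number is unknown, and anyone with missing age.
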